### **9.4.4 Vital signs**

Where supine blood pressure and pulse rate are measured in triplicate, the mean value will be calculated and used in all subsequent calculations.

Vital signs data will be summarized by treatment, group, and dose level, together with changes from baseline, where baseline is defined as the mean of the triplicate Day 1 predose assessment.

Figures of mean vital signs and mean changes from baseline profiles will be presented by treatment.

Values for individual participants will be listed.

#### **9.4.5    Electrocardiogram (ECG)**

ECGs will be performed for safety monitoring purposes only and will not be presented. Any clinically significant findings from ECGs will be reported as an AE.

#### **9.4.6    Immunogenicity Assessments**

The frequency and percentage of participants with preexisting ADAs and with treatment-emergent ADAs (TE ADA) to ramucirumab will be tabulated and listed by treatment.

For participants who are ADA negative at baseline, TE ADAs are defined as those with a titer 2-fold (1 dilution) greater than the minimum required dilution of the assay (1:10). For participants who are ADA positive at baseline, TE ADAs are defined as those with a 4-fold (2 dilution) increase in titer compared to baseline. The frequency and percentage of participants with neutralizing antibodies will also be tabulated for participants with TE ADA+.

The relationship between the presence of antibodies and the PK parameters, including safety to ramucirumab, may be assessed. All immunogenicity analysis will be performed and reported by Eli Lilly.

#### **9.4.7    Hypersensitivity reactions**

For all drug hypersensitivity reactions that occur, additional follow-up data will be collected to assess the patient's medical history, alternative causes, and symptoms.

These data will be listed.

#### **9.4.8    Injection-Site Reactions**

Injection-site reaction data (including erythema, induration, pain, pruritus, edema, and bleeding) will be listed and summarized by treatment in frequency tables. The exploratory ISR data collected from the Scarletred tool at the same timepoints will be reported separately.

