Procedures/ Assessments	Screening	Baseline	Inpatient								Outpatient		EoT	F/U				Comments
			Dosing													ED		
Visit	1	2	3								4	5	6	7	8	9	10	
Study Day	-28 to -2	-1	1	2	3 ±1	4 ±1	5 ±1	6 ±1	7 ±1	8 ±1	12 ±1	15 ±1	22 ±1	31 ±2	40 ±2	50 ±3	90 ±3	
Week	-4		1	1	1	1	1	1	1	2	2	3	4	5	6	8	12	
Injection site reaction assessments			X (Predose; 1 min ± 1 min, 10 min ± 2 min, 30 min ± 5 min, and 240 min ± 10 min postdose)	X (24 hr ± 4 hr postdose)	X	X	X	X	X	X	X	X	X	X	X	X	X	Injection site assessments will be performed at the indicated time points on each study day. The findings from the assessment are recorded on the ISR questionnaire. Injection site pain (ISP) assessments are part of the solicited and spontaneous ISR assessments. All positive responses of pain require an additional assessment using the Pain Visual Analog Scale (Pain VAS). If there are 2 injections, the ISR questionnaire will be filled out separately for each site, after both injections have been administered. The exploratory tool for injection site assessment (Scarletred) will be performed after each time the ISR questionnaire is administered for each injection. ISR assessments will be performed for the SC groups only. See Section 8.2.5 for details.

Abbreviations: AE = adverse event; BP = blood pressure; CRU = clinical research unit; CTCAE = Common Terminology Criteria for Adverse Events; ECG = electrocardiogram; ED = early discontinuation; EoT = end of treatment; F/U = follow-up; FSH = follicle-stimulating hormone; HIV = human immunodeficiency virus; I/E = inclusion/exclusion; Ig = immunoglobulin; ISP = injection site pain; ISR = injection site reaction; IV = intravenous; P = predose; PK = pharmacokinetic; PR = pulse rate; SC = subcutaneous; TB = tuberculosis; TST = tuberculin skin test; VAS = visual analog scale.

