## 4. STUDY OBJECTIVES AND ENDPOINTS

### 4.1 Primary Objectives and Endpoints

Primary Objectives	Primary Endpoints

Evaluate ramucirumab safety following a single dose in healthy participants

	

Incidence of adverse events (AEs), treatment-emergent adverse events (TEAEs), and serious adverse events (SAEs) after intravenous (IV) administration and subcutaneous (SC) administration in healthy participants

Assess injection site reactions (ISRs) following SC administration of ramucirumab using ISR questionnaire

	

Characterization and measurement of incidence and severity of ISRs (including injection site pain [ISP]) using data collected from the ISR questionnaire

Assess ramucirumab PK following a single dose of IV or SC administration

	

PK parameters:

IV: area under the concentration versus time curve (AUC) from zero to infinity (<math>AUC_{[0-\infty]}</math>), maximum observed drug concentration (<math>C_{max}</math>), time of maximum observed drug concentration (<math>t_{max}</math>)

SC: <math>AUC_{(0-\infty)}</math>, <math>C_{max}</math>, <math>t_{max}</math> after SC administration

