The SC injection site will be the abdomen.

[figure not shown]
There will be at least a 2-week safety observation period between the titrating SC injection groups (Groups 1 and 2), and between the SC and IV 700-mg groups (Group 2 and 3) while local laboratory data is reviewed by the sponsor and investigator. If the safety review is acceptable, Groups 4 and 5 may be dosed simultaneously to Group 3, as no dose escalation is occurring in those groups. Group 6 will be dosed with an infusion pump once the sponsor has reviewed both the safety and PK data (Groups 1 through 3) and thus confirm the dose for Group 6 (maximum dose 1400 mg).

Following the safety review of Groups 1 and 2, the sponsor and investigator agreed to allow doses to be reduced for remaining groups. This may mean less groups may need to be studied. The asymptomatic transaminase increases observed during the safety review have also lead to a change in the exclusion criteria to further enhance the safety of the participants. In view of these findings, subsequent doses will be capped at 350 mg. Lower doses may also be studied. These decisions will be based on emerging data.

Injection site pain and ISRs will be monitored in each group, and a comparison of scorings will be used. The severity of ISP and ISRs reported across all participants will be evaluated. The data from Group 1, in comparison to Groups 4 and 5, will provide insight about the effect of injection volumes and ramucirumab concentration on ISP and ISR.

Participants will be discharged from the CRU on Day 8 after all study assessments have been completed and in agreement with the investigator. Participants may be required to remain in the CRU longer than Day 8, at the investigator's discretion. Participants will be required to return to the CRU for clinical assessments and blood samples on an outpatient basis until the final follow-up visit approximately 12 weeks following the IV infusion or SC injection.

The study schema is shown below.

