## 6. TREATMENTS

The following is a list of the study treatment names that will be used in the TFLs.

Study Treatment Name	Abbreviations	Treatment order in TFL
Placebo IV	A	1
Placebo SC	B	2
350 mg ramucirumab IV	C	3
350 mg ramucirumab SC (1x2 mL)	D	4
350 mg ramucirumab SC (2x2 mL)	E	5
350 mg ramucirumab SC (2x1 mL)	F	6
700 mg ramucirumab SC (2x2 mL)	G	7
XX mg ramucirumab slow SC infusion	H	8

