## 9. STATISTICAL METHODOLOGY

### 9.1 General

Data listings will be provided for all data that is databased. Summary statistics and statistical analysis will only be presented for data where detailed in this SAP. For continuous data, summary statistics will include the arithmetic mean, arithmetic standard deviation (SD), median, minimum, maximum and N; for log-normal data (e.g. the PK parameters: AUCs and  $C_{max}$ ) the geometric mean and geometric coefficient of variation will also be presented. For categorical data, frequency count and percentages will be presented. Data listings will be provided for all participants up to the point of withdrawal, with any participants excluded from the relevant population highlighted. Summary statistics and statistical analyses will generally only be performed for participants included in the relevant analysis population. For the calculation of summary statistics and statistical analysis, unrounded data will be used.

Mean change from baseline is the mean of all individual participants' change from baseline values. Each individual change from baseline will be calculated by subtracting the individual participant's baseline value from the value at the timepoint. The individual participant's change from baseline values will be used to calculate the mean change from baseline using a SAS procedure such as Proc Univariate.

Data analysis will be performed using SAS® Version 9.4 or greater.

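### The ISR tables have no stated unit or denominator and one SC placebo column, so participant-level counts would confound Group 1 versus Groups 4 and 5 with number of injection sites

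*SAP*

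**What the plan says.** SAP 4.1 makes ISRs a primary endpoint: "Characterization and measurement of incidence and severity of ISRs (including injection site pain [ISP]) using data collected from the ISR questionnaire". The tabulation rule in SAP 9.4.8 is that the data "will be listed and summarized by treatment in frequency tables". SAP 9.1 adds "For categorical data, frequency count and percentages will be presented". Neither section says whether a percentage is of participants, sites or reactions, or how two sites in one person are combined.

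The treatment labels in SAP 6 include "350 mg ramucirumab SC (1x2 mL") for Group 1, "350 mg ramucirumab SC (2x2 mL") for Group 4 and "350 mg ramucirumab SC (2x1 mL") for Group 5. Group 2 also has two injections. All SC placebo has one label, although Protocol 6.1 gives SC placebo by injection in Groups 1, 2, 4 and 5 and by pump in Group 6. Protocol 6.1 also places a second injection in a different quadrant.

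The data are collected by site. The Schedule of Activities (Protocol 1.3) states: "If there are 2 injections, the ISR questionnaire will be filled out separately for each site, after both injections have been administered".

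SAP 5 states the comparison to be made: "The data from Group 1, in comparison to Groups 4 and 5, will provide insight about the effect of injection volumes", and goes on to name concentration as well, with ISP and ISR as the outcomes. By contrast, the adverse event, clinical chemistry and haematology, and vital sign summaries (SAP 9.4.1, 9.4.3, 9.4.4) are split by group and dose level as well as by treatment.

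**The concern.** Volume and concentration act at the site of injection. Per site, Groups 1 and 4 share 2 mL and differ in concentration, while Groups 1 and 5 share 175 mg/mL and differ in volume. A participant with two sites has two chances of a reaction. If a participant counts as a case when either site reacts, Groups 4 and 5 will tend to show more ISRs than Group 1 even when every injection carries the same risk. A reader could take that excess for an effect of concentration or volume.

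The single placebo column has a related problem. Its rate reflects a blend of regimens that matches neither Group 1 nor the two-site groups. Active-minus-placebo differences would then lean downwards for Group 1 and upwards for the two-site groups.

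The adverse event tables cannot make up for this, because Protocol 8.2.5 records an ISR as an AE only if it is severe. The descriptive ISR tables are the planned analysis of this endpoint.

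**Working it through.** **Plan's own figures.** No ISR rate or precision is stated. The nearby sample size figures reproduce: 6 groups × 10 = 60 enrolled, and 6 × 8 = 48 evaluable.

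**Inputs from the documents.** Each group has 7 active and 3 placebo participants (SAP 7). There is one site in Group 1 and two in Groups 2, 4 and 5 (SAP 5 and 6).

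**Assumptions.** The per-site ISR probability p is the same at every site, so there is no true effect of drug, volume or concentration. The correlation between two sites in one person is rho, taken from 0 to 1. Each placebo participant receives the same number of injections as the active participants in that group.

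**Any-site incidence with two sites:** P = 1 − [(1 − p)² + rho·p(1 − p)]. With one site it is p.

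- p = 0.10, rho = 0: 1 − 0.81 = 0.19
- p = 0.10, rho = 0.5: 1 − (0.81 + 0.045) = 0.145
- p = 0.10, rho = 1: 1 − (0.81 + 0.09) = 0.10
- p = 0.30, rho = 0: 1 − 0.49 = 0.51
- p = 0.30, rho = 0.5: 1 − (0.49 + 0.105) = 0.405
- p = 0.30, rho = 1: 1 − (0.49 + 0.21) = 0.30

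**Pooled injection placebo.** There are 3 one-site participants (Group 1) and 9 two-site participants (Groups 2, 4 and 5), so the pooled rate is (3p + 9P)/12. For p = 0.10 and rho = 0 this is (0.30 + 1.71)/12 = 0.1675.

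| p | rho | One site | Two sites | Pooled injection placebo |
|---|---|---|---|---|
| 0.10 | 0 | 10% | 19% | 16.8% |
| 0.10 | 0.5 | 10% | 14.5% | 13.4% |
| 0.10 | 1 | 10% | 10% | 10% |
| 0.30 | 0 | 30% | 51% | 45.8% |
| 0.30 | 0.5 | 30% | 40.5% | 37.9% |
| 0.30 | 1 | 30% | 30% | 30% |

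Over p from 0.05 to 0.70, the two-site to one-site ratio is 1.30 to 1.95 at rho = 0, 1.15 to 1.48 at rho = 0.5, and 1.0 at rho = 1. If reactions rather than participants are counted, the expected number per person doubles from p to 2p whatever rho is.

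**Active minus pooled placebo with no drug effect, p = 0.10.** At rho = 0, Group 1 shows 10 − 16.75 = −6.75 points and a two-site group shows 19 − 16.75 = +2.25 points. At rho = 0.5 these are 10 − 13.375 = −3.4 and 14.5 − 13.375 = +1.1 points.

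**Group 6.** The documents do not give the number of pump sites. If Group 6 runs and one site is assumed, the pooled placebo at p = 0.10 and rho = 0 is (0.30 + 1.71 + 0.30)/15 = 15.4%.

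**In participants.** At p = 0.30 and rho = 0, the expected number with an ISR among 7 active is 7 × 0.30 = 2.1 in Group 1 and 7 × 0.51 = 3.6 in Group 4 or 5.

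**With sites as the denominator,** the expected rate is p in every group, so the artefact disappears. At full enrolment there are 7 active sites in Group 1, 14 in each of Groups 4 and 5, and 3 + 18 = 21 injection placebo sites.

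**The case against.** The SAP does not say that ISRs will be counted per participant. Tabulation by treatment names the columns, not the unit, and a per-site table would fit the same sentence. SAP 3 refers to a separate TFL shell document, not available here, that may define the denominators. The ISR data will be listed, so per-site rates should be recoverable. Active regimens are not pooled, and their labels show the number of injections. Group 4 versus 5 and Group 2 versus 4 have equal numbers of sites and are not affected. With 7 active participants per group, the artefact amounts to about one or two people. A participant-level rate is also a legitimate measure of how a whole dose is tolerated.

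Most of this stands, and it limits the point. A reader might infer that the ISR tables are bound to differ through number of sites alone. The documents do not support that: it needs participant-level or reaction-level counting, which they do not specify, and for any-site incidence it also needs sites that are not perfectly correlated. A reader might also carry the calculation over to the pain VAS in SAP 9.4.9. The any-of-two formula does not apply to an intensity score, and Protocol 8.2.5, which ties timing to the second injection, does not clearly establish that each site is scored separately.

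Two things survive. The unit for a primary endpoint is undefined in the SAP. The single SC placebo label is a stated rule, and SAP 9.4.8 lacks the split by group that other safety summaries have.

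**Conclusion.** The point holds conditionally. If ISR incidence is counted per participant at any site, the comparison of Group 1 with Groups 4 and 5 is confounded with number of sites. At p = 0.10 the spurious gap is 9 points for independent sites, 4.5 at a correlation of 0.5 and none at 1. At p = 0.30 it is 21, 10.5 and 0 points. The mixed placebo column follows from the text as written, assuming placebo matches its group's injections, and its numerical effect depends on the same counting rule. Both p and rho are assumptions.

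No test or sample size is affected, since SAP 9.4.11 plans no inferential safety analysis. What is at stake is the descriptive reading of a primary endpoint in a comparison that the plan says it will make.

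**What to change.** In SAP 9.4.8, state the unit and denominator. For Groups 1, 4 and 5, report ISR incidence and severity per injection site alongside participant-level any-site incidence. Show SC placebo by number of injections beside the pooled column, with pump placebo separate if Group 6 runs. Cluster any interval by participant, because two sites in one person are not independent. Apply the same to SAP 9.4.9 only if the VAS is scored per site.

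This is a cheap improvement: the questionnaire is already completed per site, so no new ISR data are needed. There are three limits. The one-site placebo column has only 3 participants. The two-site placebo column still combines 2×2 mL with 2×1 mL. A per-site display also leaves the difference in dose per site, 350 mg in Group 1 against 175 mg in Groups 4 and 5 (2 mL × 87.5 mg/mL and 1 mL × 175 mg/mL), which is built into the design.

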#### **9.4.9    Injection-Site Pain Assessment**

Intensity of pain data will be quantified using a 100-mm validated VAS where 0 mm represents "no pain" and 100 mm represents "worst possible pain". The data will be summarized and listed by treatment and timepoint.

#### **9.4.10    Other assessments**

All other safety assessments not detailed in this section will be listed but not summarized or statistically analyzed.

#### **9.4.11 Safety and Tolerability Statistical Methodology**

No inferential statistical analyses are planned.

### **10. INTERIM ANALYSES**

No interim analyses are planned for this study. If an unplanned interim analysis is deemed necessary for reasons other than a safety concern, the protocol must be amended.

However, there will be periodic reviews of data to assess safety, tolerability, and PK data. There will be sentinel dosing in this protocol, the initial 2 participants will be randomized/dosed (1 ramucirumab:1 placebo), and subsequently (the next day), the remaining participants in the group will be dosed. The following information belongs in this section:

- Safety reviews are planned prior to dose escalation after 2-week safety data are available.
- The Lilly PK team will review the PK data for Groups 1 and 2 if timing permits.
- The Lilly PK team will review the PK data once Group 1 through 3 PK samples have been collected (cutoff 2-week sample collection in Group 3).

### **11. CHANGES FROM THE PROTOCOL SPECIFIED STATISTICAL ANALYSES**

There were no changes from the protocol specified statistical analyses.

### **13. DATA PRESENTATION**

#### **13.1 Derived Parameters**

Individual derived parameters (e.g. PK parameters) and appropriate summary statistics will be reported to three significant figures. Observed concentration data, e.g.  $C_{max}$ , should be reported as received. Observed time data, e.g.  $t_{max}$ , should be reported as received. N and percentage values should be reported as whole numbers. Median values should be treated as an observed parameter and reported to the same number of decimal places as minimum and maximum values.

#### **13.2 Missing Data**

Missing data will not be displayed in listings.

---

### 13.3 Insufficient Data for Presentation

Some of the TFLs may not have sufficient numbers of participants or data for presentation. If this occurs, the blank TFL shell will be presented with a message printed in the center of the table, such as, "No serious adverse events occurred for this study."

Leo Document ID = 8693ba9d-9c40-43f9-ba20-0708383e5959

Approver: PPD

Approval Date & Time: 23-Nov-2020 15:52:32 GMT

Signature meaning: Approved

Approver: PPD

Approval Date & Time: 23-Nov-2020 16:19:02 GMT

Signature meaning: Approved

Approver: PPD

Approval Date & Time: 23-Nov-2020 16:19:32 GMT

Signature meaning: Approved

Approver: PPD

Approval Date & Time: 25-Nov-2020 09:02:42 GMT

Signature meaning: Approved
